### **8.3.4 Additional Analyses of the Primary Efficacy Endpoint(s)**

Sensitivity analysis for the primary endpoint of ppFEV1 will be conducted using all spirometry data as collected if there are at least 5% of the total subjects in each study part who have at least one post-Baseline inconsistent use of bronchodilator medications and/or airway clearance.

## **8.4 Secondary Efficacy Analyses**

Efficacy analyses will be performed by treatment group at each protocol-specified visit on each of the secondary efficacy endpoints including

- absolute change from Baseline through Day 29 in Sweat Chloride (in mmol/L),

- absolute change from Baseline through Day 29 in FVC (in L), FEF25-75 (in L/s), and
- relative change, calculated as percent change, from Baseline through Day 29 in ppFEV1, FVC, and FEF25-75

The point estimate for each of the secondary efficacy endpoints from the MMRM model along with the 95% confidence intervals and the corresponding p-values will be presented. In addition, pairwise comparison of each active treatment group versus placebo group will be analyzed using MMRM method as described in Section 8.3.3.

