- ✓ 9. ppFEV₁ ≥ 40% and ≤ 90% of predicted normal for age, gender, and height (Global Lung Function Initiative [GLI] equations) at Screening
- ✓ 10. SwCl at the Screening visit must be ≥ 60 mmol/L. For subjects who participated in Study M19-771, it is acceptable to use the SwCl value that the central lab provided from the screening visit in Study M19-771 to establish eligibility.

Subject History

- ✓ 11. Stable pulmonary status, i.e., no respiratory infections or exacerbations requiring a change in therapy (including antimicrobials) or causing an acute decline in ppFEV₁ of > 10% from usual baseline within 4 weeks prior to Day 1 (first dose of study drug).
- ✓ 12. Absence of comorbidities and medical history items listed below, or others that, in the opinion of the investigator, may pose additional risk by participating in the study, or may confound the results of the study.
 - a. Cirrhosis with portal hypertension (e.g., splenomegaly, esophageal varices)
 - b. Past or present positive sputum culture for organisms that are often associated with a faster decline in pulmonary status (e.g., *Mycobacterium abscessus*, *Burkholderia cenocepacia* or *B. dolosa*, *Aspergillus fumigatus* infection or allergic bronchopulmonary aspergillosis [ABPA]) is allowed if, in the opinion of the investigator, clinical stability has not been adversely affected. Subjects with these organisms can remain on chronic treatment for them if applicable, as long as the medications are not prohibited in this study (e.g., clarithromycin, rifampin, itraconazole, see table in Section 5.3). To assure clinical stability, treatment for these organisms should start at least 8 weeks prior to screening, and the subjects will be expected to continue the treatment through the final study visit.
 - c. History of malignancy within past 5 years (except for excised basal cell carcinoma of the skin with no recurrence, or treated carcinoma in situ of the cervix with no recurrence)
 - d. Abuse of alcohol, medications, or illicit drugs within 1 year prior to Screening, per the investigator.
 - e. Smoking or vaping tobacco or cannabis products within 1 year prior to Screening.
 - f. History of solid organ or hematopoietic transplantation.
 - g. History of known sensitivity to any component of the study drug.
 - h. Need for supplemental oxygen while awake, or > 2 L/minute while sleeping.

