7.3 Statistical Analyses for Efficacy

All efficacy analyses will be conducted on the FAS based on treatment as randomized.

For the primary efficacy endpoint in both Part 1 and Part 2, the null hypothesis that the within-group absolute change from baseline in ppFEV₁ through Day 29 is zero will be tested for each treated group at 2-sided alpha of 0.05. The primary analysis will be performed using a mixed-effect model with repeated measures (MMRM) with change from Baseline in ppFEV₁ as the dependent variable; treatment group, visit, and treatment-by-visit interaction as fixed effects; subject as a random effect; and baseline ppFEV₁ as a covariate. The estimate for the within-group mean change along with the 95% confidence intervals and the corresponding *P* values will be calculated as the primary analysis. The treatment effect compared to placebo will be estimated using the same model.

The secondary endpoints of sweat chloride, ppFEV₁, FVC, and FEF₂₅₋₇₅ will be analyzed based on an MMRM model similarly as the primary endpoint.

Details on the efficacy analyses are provided in the SAP.

Sample Size Estimation

The power calculations are provided for the most potentially efficacious groups with the combination treatment for both Part 1 and Part 2 for the primary efficacy endpoint. Placebo groups from both Part 1 and Part 2 will be combined in the Part 2 efficacy analysis. A sample size of 18 subjects in a group will provide 80% power to detect a 5.3% absolute increase from baseline in ppFEV₁ for that group assuming a standard deviation of 7.5%. When comparing to the placebo group, a sample size of 18 subjects in both treated group and placebo group will provide 80% power (Part 1), or a sample size of 18 subjects in treated group and 27 subjects in placebo group will provide approximately 87% power (Part 2), to detect a 7.3% effect size in ppFEV₁ change from Baseline assuming the standard deviation of 7.5% for change in ppFEV₁ for both groups.

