3.12 Sweat Collection

Sweat collection will be performed to evaluate sweat chloride (SwCl). Sweat chloride concentration is a biomarker of CFTR ion channel function. It is a sensitive, standardized and non-invasive measure to assess systemic CFTR modulator effects. Chloride concentration will be measured in sweat collected by an approved collection device provided to sites by a central provider and according to the 2009 guidelines issued by the Clinical and Laboratory Standards Institute.

To ensure consistency and reproducibility in this multicenter study, trained clinical study centers will collect sweat according to procedures as outlined in the lab manual. Two sweat collections, one from

each arm, will be obtained from each subject at the time points indicated in the protocol activity schedule. Sweat samples will immediately be frozen and sent to the central laboratory for testing and interpretation of results.

The clinical study center should be encouraged to select subjects for the study for which it is known that adequate quantities of sweat can be collected.

The sites will be provided with sweat collection equipment and kits, and a central laboratory will act as central readers for SwCl. Sweat collection will be measured beginning at Screening and as specified in Section 2.

To prevent the potential unblinding, site personnel and subjects will not be informed of the subjects' study-related post-first-dose sweat chloride results until the end of the corresponding study part (Part 1 or Part 2).

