## **8.0 Efficacy Analyses**

### **8.1 General Considerations**

All efficacy analyses will be conducted for the FAS. All tests will be 2-sided at an alpha level of 0.05. For each part of the study, the efficacy analysis will be performed after all ongoing subjects have completed the study part and the database has been locked.

For the primary efficacy endpoint, the null hypothesis that the within-group absolute change from baseline in ppFEV1 through Day 29 is zero will be tested for each treated group at 2-sided alpha of 0.05.

Unless otherwise specified, any subject who is randomized based on a wrong stratum will be analyzed according to the actual stratum to which the subject belongs.

"Baseline" refers to the last non-missing observation before the first administration of study drug.

Unless otherwise specified, continuous variables will be analyzed using Mixed-Effect Model Repeat Measurement (MMRM) method with the model based mean and standard error being provided. The Baseline and visit means will also be presented for each treatment group among subjects who have both Baseline and at least one post Baseline visit values. Treatment groups will be compared using MMRM model as described in Section 8.2. Point estimates and 95% CIs of mean change from Baseline within each treatment group, the difference between each active treatment group and placebo, and the difference between each combination therapy arm and the ABBV-3067 150 mg monotherapy arm (Part 1 only) will be provided. Note that both placebo arms in Part 1 and Part 2 will be combined into one placebo group for the Part 2 model comparison.

Plots of the primary endpoint and certain secondary endpoints by treatment group will be used to visualize the change of endpoint values over time and the difference between treatment groups.

Use of bronchodilator medications and/or airway clearance techniques may affect lung function measurements in the short term. Therefore, post-baseline spirometric measurement that are collected inconsistently with the conditions for the baseline spirometric measurement will be excluded from the efficacy analysis. For example, if baseline spirometric measurement was collected prior to bronchodilator use, then any spirometric measurement collected post bronchodilator use at a subsequent visit will be excluded from analysis.

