## **8.2 Handling of Missing Data**

The primary endpoint and key secondary endpoints will use the same analysis method: Mixed-Effect Model Repeat Measurement (MMRM). This modeling approach handles partially missing dependent variables (change from Baseline to one of the visits is missing) based on the assumption of data being missing at random. No other imputation will be used.

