### **8.3.3 Primary Efficacy Analysis**

The primary analysis will be performed using MMRM with change from Baseline in ppFEV1 as the dependent variable. The mixed model includes the categorical fixed effects of treatment, visit and treatment-by-visit interaction, as well as the continuous fixed effect of baseline ppFEV1. The random effects of the model will be subject ID. Parameter estimation will use the method of restrictive maximum likelihood (REML).

The point estimate for the primary endpoint from the MMRM model along with the 95% confidence interval and the corresponding p-value will be presented for the primary efficacy analysis. The pairwise comparison of the primary endpoint of ppFEV1 between each active treatment group versus the placebo group will also be estimated using the same model. The Least Squares Mean of the treatment difference between each active treatment group versus the placebo group will be presented along with the 95% confidence interval and a 2-sided p-value.

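### Read literally, the SAP adjusts sweat chloride, FVC and FEF25-75 for baseline ppFEV1 and not for each endpoint's own baseline, which costs precision

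*SAP*

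**What the plan says.** **Model for the secondary endpoints.** SAP 8.4 covers change in SwCl, FVC and FEF25-75, and percent change in ppFEV1, FVC and FEF25-75. For the comparisons with placebo it states that "pairwise comparison of each active treatment group versus placebo group will be analyzed using MMRM method as described in Section 8.3.3".

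**The model referred to.** SAP 8.3.3 has treatment, visit and their interaction, "as well as the continuous fixed effect of baseline" ppFEV1, and subject as a random effect. No other covariate appears.

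**Other places that could change this.** SAP 8.1 points treatment comparisons to SAP 8.2, which says that the primary and key secondary endpoints share the MMRM method but names no covariate. Protocol 7.3 says that the secondary endpoints "will be analyzed based on an MMRM model similarly as the primary endpoint". SAP 7.1 lists baseline SwCl, FVC and FEF25-75 among the continuous characteristics to be summarised, so the variables will exist.

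**How a SwCl value is formed.** Operations Manual 3.12 (protocol Appendix F) takes two sweat collections, one from "each arm, will be obtained from each subject at the time points indicated in the protocol activity schedule" (arm here means limb). SAP 8.1 says that Baseline "refers to the last non-missing observation before the first administration of study drug". Neither document says how two results from one visit become one value, at Baseline or later.

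**The concern.** A programmer who follows the cross-reference fits change in SwCl with baseline ppFEV1 as the covariate. Baseline SwCl, the obvious predictor of later SwCl, is left out. The same holds for FVC and FEF25-75. Relative change in ppFEV1 is unaffected, because there the named covariate is the right one.

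SwCl is the first-listed secondary endpoint, and the clinical hypothesis in protocol 2.1 names it beside lung function. Arms have 9 or 18 subjects, and SAP 8.1 compares each combination with the 150 mg monotherapy arm, planned at 9. Randomisation is stratified on screening ppFEV1 only, so nothing in the design balances baseline SwCl. What is at stake is the width of the intervals used to compare dose levels. There is also a pre-specification issue: the covariate, and possibly the visit value, could still be chosen after unblinding.

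**Working it through.** 1. **The plan's own figures.** The only power statements (protocol 7.3, SAP 2.4) are for ppFEV1, with SD 7.5 points. With the noncentral t at two-sided alpha 0.05:
   - one group of 18, 5.3 points: 80.7% (plan: 80%)
   - 18 versus 18, 7.3 points: 81.0% (plan: 80%)
   - 18 versus 27, 7.3 points: 87.8% (plan: about 87%)

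   They reproduce, but they say nothing about SwCl. The documents give no SwCl SD, correlation or power, so everything below is assumption shown as a range.

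2. **Model for SwCl.** Let Baseline, Day 15 and Day 29 each have variance 1 and the same correlation r between any two visits. Assume that baseline ppFEV1 is unrelated to the change. Take M as the mean of Days 15 and 29.
   - Variance of M is (1 + r)/2.
   - Variance of the change M − Baseline is (1 + r)/2 + 1 − 2r = 1.5(1 − r). This is the residual variance as written.
   - With own baseline as covariate it is (1 + r)/2 − r² = (1 − r)(1 + 2r)/2.
   - The ratio is (1 + 2r)/3. For a single post-baseline visit it is (1 − r²)/[2(1 − r)] = (1 + r)/2.

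3. **Results.** The SE falls by 1 − √ratio. The last column starts from a comparison with 80% power as written: Φ[(1.96 + 0.8416)/√ratio − 1.96], using the mean of Days 15 and 29.

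| r | Ratio, mean of Days 15 and 29 | SE lower by | Ratio, one visit | SE lower by | 80% power becomes |
|---|---|---|---|---|---|
| 0.5 | 0.667 | 18.4% | 0.75 | 13.4% | 93% |
| 0.7 | 0.800 | 10.6% | 0.85 | 7.8% | 88% |
| 0.9 | 0.933 | 3.4% | 0.95 | 2.5% | 83% |

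4. **Bias and type I error.** The Part 1 layout (arms of 9, 9, 9, 18, 18, 18, 18, 18) was simulated 4,000 times at each r from 0.3 to 0.9, with no treatment effect and an unrelated baseline ppFEV1. The comparison of Regimen G with placebo, adjusted for ppFEV1, was centred on zero, and its type I error was 4.6% to 5.3%. The SD of the estimate was 0.293 as written against 0.238 with own baseline at r = 0.5 (variance ratio 0.66; formula 0.67). At r = 0.7 it was 0.221 against 0.199 (0.81; formula 0.80).

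5. **If baseline ppFEV1 does predict SwCl change.** A correlation c removes c² of the variance, so the ratio becomes [(1 + 2r)/3]/(1 − c²). With c = 0.3, 1 − c² = 0.91:
   - r = 0.5: 0.667/0.91 = 0.733, SE 14.4% lower
   - r = 0.7: 0.800/0.91 = 0.879, SE 6.2% lower
   - r = 0.9: 0.933/0.91 = 1.026, SE 1.3% higher

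6. **Two collections.** This applies only if a single collection served as Baseline while later visits used the mean of both. Let w be the same-visit correlation between the two collections, r the correlation between single collections at different visits, and v = (1 + w)/2. With own-baseline adjustment the residual variance is (v + r)/2 − r² for a single-collection Baseline and (v + r)/2 − r²/v for an averaged one. For r = 0.5 to 0.7 and w = 0.80 to 0.95, averaging lowers the SE by 0.7% to 9%.

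**The case against.** The best reply is that SAP 8.3.3 is a template. Its dependent variable is also ppFEV1 change, so SAP 8.4 works for SwCl only if the reader substitutes the endpoint, and whoever substitutes the outcome would naturally substitute its baseline too. Protocol 7.3 fits this, and SAP 7.1 already plans for the baseline variables. This stands as far as intent goes: own-baseline adjustment may well be what was meant. But no sentence says so, and protocol 7.1 leaves such details to the SAP. The text is under-specified at least as much as it is wrong.

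Three stronger readings are tempting, and the documents do not support them.

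- **That the SwCl comparison is invalid.** Randomised comparisons remain unbiased with correct type I error. Only precision is lost.
- **That chance imbalance in baseline SwCl goes wholly uncorrected.** The endpoint is a change score, so each subject's baseline is already subtracted. Under the model above, the slope of change on baseline is r − 1, so a baseline difference d between arms leaves (1 − r)d, with reversed sign: half of d at r = 0.5, a tenth at r = 0.9.
- **That the Baseline rule throws away one of the two sweat collections.** This requires each collection to count as a separate observation, which the SAP does not say. Protocol 5.1, on subjects from Study M19-771, says "it is acceptable to use the SwCl value that the central lab provided from the screening visit", and SAP 7.1 likewise treats baseline SwCl as one value. Operations Manual 3.12 refers to a lab manual for collection procedures. That manual is not among the documents and may define one value per visit.

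It is also fair to say that dose selection rests on safety, tolerability, efficacy and pharmacokinetics together, with no stated SwCl rule that turns on interval width.

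**Conclusion.** The point holds as a gap in specification that costs precision. As written, the SwCl, FVC and FEF25-75 models carry baseline ppFEV1 and omit the endpoint's own baseline. For SwCl the avoidable loss is about 18% of the SE at a visit-to-visit correlation of 0.5, falling to about 3% at 0.9.

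That range rests on equal variances and correlations across visits, on reading the endpoint as the mean of Days 15 and 29, and on a baseline ppFEV1 unrelated to SwCl change. If ppFEV1 is moderately related to the change and the visit correlation is near 0.9, the gain disappears. The true size cannot be fixed from the documents. FVC and FEF25-75 share the gap in wording, but no size was computed for them. The check on bias and type I error used the randomised Part 1 layout. The Part 2 comparison with pooled placebo, where 18 of the planned 27 controls come from Part 1, was not simulated.

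The handling of the two sweat collections is a minor clarification: a missing rule, not a demonstrated error.

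**What to change.** In SAP 8.4, state that each secondary MMRM uses the baseline value of its own endpoint (SwCl, FVC or FEF25-75) as the continuous covariate in place of baseline ppFEV1.

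Unless the laboratory manual already defines the SwCl visit value, in which case a citation is enough, add one rule to SAP 8.1 for Baseline and all later visits. An example is the mean of the evaluable collections at that visit, or the single result if only one is evaluable.

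Both changes should be made before unblinding of any study part not yet analysed. The cost is two sentences; no new data are needed.

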## **8.5 Additional Efficacy Analyses**

There are no additional efficacy analyses planned for this study.

## **8.6 Efficacy Subgroup Analyses**

Descriptive statistics of the primary endpoint will be provided for the following subgroups to evaluate the consistency of the efficacy across subgroup levels.

- Geographic region (North America, Rest of World)
- Stratification factor of screening ppFEV1 (< 70%, ≥ 70%)
- Prior use of CFTR modulators (Yes, No)

The point estimates and 95% CIs will be provided within each subgroup level. No p-value will be provided for subgroup analysis.

## **9.0 Safety Analyses**

### **9.1 General Considerations**

Safety data will be summarized for the Safety Analysis Set for each part of the study. Safety summaries will be presented by treatment arm, as well as for the combined placebo arms from Part 1 and Part 2.

For the safety analysis, subjects are assigned to a treatment group based on the treatment actually received, regardless of the treatment randomized. If a subject received more than one treatment, the subject will be grouped in the treatment group for which they received the most doses. All safety analyses will be based on observed data. Missing safety data will not be imputed.

## **9.2 Adverse Events**

Adverse events (AEs) will be summarized and presented using primary MedDRA System Organ Classes (SOCs) and preferred terms (PTs) according to the version of the MedDRA coding dictionary used for the study at the time of database lock. The actual version of the MedDRA coding dictionary used will be noted in the AE tables and in the clinical study report. Specific adverse events will be counted once for each subject for calculating percentages, unless stated otherwise. In addition, if the same adverse event occurs multiple times within a subject, the highest severity and level of relationship to investigational product will be reported.

### **9.2.1 Treatment-Emergent Adverse Events**

Treatment-emergent (TE) AEs are defined as any AE with an onset date that is after the first dose of study drug and no more than 30 days after the last dose of study drug. Events where the onset date is the same as the study drug start date are assumed to be treatment-emergent. All TEAEs will be summarized overall, as well as by primary MedDRA SOC and PT. The SOCs will be presented in alphabetical order, and the PTs will be presented in alphabetical order within each SOC.

The number and percentage of subjects experiencing TEAEs will be summarized.

Pre-treatment AEs will be summarized separately in listing format.

AEs starting more than 30 days following the last dose of study drug will be summarized separately in listing format.

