- Discontinuation or interruption of study drug due to a hepatic-related AE, including laboratory criteria defined in Section 5.5:
- A hepatic-related SAE

Clinically Significant Assessments

Study assessments including laboratory tests, ECGs, physical examinations, and vital signs will be assessed, and those deemed a clinically significant worsening from baseline will be documented as an AE. When possible, a clinical diagnosis for the study assessment will be provided, rather than the abnormal test result alone (e.g., urinary tract infection, anemia). In the absence of a diagnosis, the abnormal study assessment itself will be listed as the AE (e.g., bacteria in urine, decreased hemoglobin).

An abnormal study assessment is considered clinically significant if the subject has one or more of the following:

- Concomitant signs or symptoms related to the abnormal study assessment
- Further diagnostic testing or medical/surgical intervention
- A change in the dose of study drug or discontinuation from the study

Repeat testing to determine whether the result is abnormal, in the absence of any of the above criteria, does not necessarily meet clinically significant criteria. The investigator will determine whether the study assessment results are clinically significant. All study assessments deemed "clinically significant" based on the investigator's medical judgment will be managed and followed to a satisfactory clinical resolution.

A laboratory value that is Grade 4 will not automatically be an SAE. A Grade 4 laboratory value will be an SAE if the clinical status of the subject indicates a life-threatening AE.

If an AE, whether associated with study drug or not, meets any of the following criteria, it is to be reported to AbbVie clinical pharmacovigilance or clinical research organization (CRO) (as appropriate) as an SAE within 24 hours after the site became made aware of the SAE (refer to Section 4.3 of the Operations Manual for reporting details and contact information):

Death of Subject	An event that results in the death of a subject.
Life-Threatening	An event that, in the opinion of the investigator, would have resulted in immediate fatality if medical intervention had not been taken. This does not include an event that would have been fatal if it had occurred in a more severe form.

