Hospitalization or Prolongation of Hospitalization	An event that results in an admission to the hospital for any length of time or prolongs the subject's hospital stay. This does not include an emergency room visit or admission to an outpatient facility.
Congenital Anomaly	An anomaly detected at or after birth, or any anomaly that results in fetal loss.
Persistent or Significant Disability/Incapacity	An event that results in a condition that substantially interferes with the activities of daily living of a study subject. Disability is not intended to include experiences of relatively minor medical significance such as headache, nausea, vomiting, diarrhea, influenza, and accidental trauma (e.g., sprained ankle).
Important Medical Event Requiring Medical or Surgical Intervention to Prevent Serious Outcome	An important medical event that may not be immediately life-threatening or result in death or hospitalization, but based on medical judgment may jeopardize the subject and may require medical or surgical intervention to prevent any of the outcomes listed above (i.e., death of subject, life threatening, hospitalization, prolongation of hospitalization, congenital anomaly, or persistent or significant disability/incapacity). Additionally, any elective or spontaneous abortion or stillbirth is considered an important medical event. Examples of such events include allergic bronchospasm requiring intensive treatment in an emergency room or at home, blood dyscrasias or convulsions that do not result in inpatient hospitalization, or the development of drug dependency or drug abuse.

All AEs reported from the time of study drug administration until 30 days or 5 half-lives after discontinuation of study drug administration will be collected, whether solicited or spontaneously reported by the subject. In addition, SAEs and protocol-related nonserious AEs will be collected from the time the subject signs the study-specific informed consent.

AbbVie will be responsible for suspected unexpected serious adverse reactions (SUSAR) reporting for the investigational medicinal product (IMP) in accordance with global and local requirements.

Adverse events will be monitored throughout the study to identify any of special interest that may indicate a trend or risk to subjects.

Adverse Events of Special Interest

Rash is an AE of special interest (AESI) and will be monitored during the study.

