7.4 Statistical Analyses for Safety

All safety analyses will be performed on the safety analysis set for both Part 1 and Part 2 based on the treatment subjects actually receive. Safety will be assessed by AEs, AESIs, weight, vital signs, clinical laboratory data, 12-lead ECGs, pulse oximetry and spirometry. Details on the safety analyses are provided in the SAP.

AEs will be coded using Medical Dictionary for Regulatory Activities (MedDRA). A treatment-emergent adverse event (TEAE) is defined as an AE with an onset date on or after the first dose of study drug and within 30 days after the last dose of study drug. The number and percentage of subjects experiencing TEAEs will be tabulated using MedDRA system organ class (SOC) and preferred term (PT), as well as by severity and by relationship to the study drug as assessed by the investigator. Summaries (i.e., number and percentages) of TEAEs, SAEs, deaths, AEs leading to discontinuation, and AESIs will be provided.

For laboratory test and vital signs variables, mean change from baseline and percentage of subjects with evaluations meeting criteria for predefined potentially clinically significant (PCS) values will be summarized.

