4.2 Recording Data and Analyses of Safety Findings

AEs will be coded using the Medical Dictionary for Regulatory Activities (MedDRA). The number and percentage of subjects with treatment-emergent adverse events (i.e., any event that begins or worsens in severity after initiation of study drug through 30 days post-study drug dosing) will be tabulated by primary MedDRA System Organ Class (SOC) and preferred term (PT). The tabulation of the number of subjects with treatment-emergent AEs by severity grade and relationship to study drug also will be provided. Subjects reporting more than 1 AE for a given MedDRA preferred term will be counted only once for that term using the most severe grade according to the severity grade table and the most related according to the relationship to study drug tables. Subjects reporting more than 1 type of AE within an SOC will be counted only once for that SOC.

Adverse Events of Special Interest

Isolated instances of nonserious, generalized, maculopapular rash have occurred in prior Phase 1 studies when ABBV-3067 and ABBV-2222 were administered together (see protocol Section 6.1). All rash AEs are considered adverse events of special interest (AESIs). These AEs have to be reported in real time (i.e., within 24 hours from the time of the knowledge of the event) using a study-specific rash questionnaire ([Appendix B](#)).

Maculopapular and other rash events are to be graded as follows (adapted from Common Terminology Criteria for Adverse Events [CTCAE] version 5.0):

- Grade 1** Macules/papules covering < 10% body surface area (BSA) with or without symptoms (e.g., pruritis, burning, tightness).
- Grade 2** Macules/papules covering 10% to 30% BSA with or without symptoms (e.g., pruritis, burning, tightness); or rash covering > 30% BSA with or without mild symptoms.
- Grade 3** Macules/papules covering > 30% BSA with moderate or severe symptoms.

Note: To calculate the percent of BSA, estimate the area covered by the actual macules/papules and do not include the clear skin between them. Imagine the rash coverage as if all of the macules and papules

coalesce into a single area. A diagram showing the contribution of different body parts to BSA, helpful to calculate % BSA, can be found at:

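### Treatment-emergent AEs are defined in two ways, and under the SAP's onset-only rule a recorded pre-dose AE that worsens on drug may be missing from the TEAE tables if it is kept as one record

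*SAP*

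**What the plan says.** Three current texts define a treatment-emergent AE.

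- SAP 9.2.1: "Treatment-emergent (TE) AEs are defined as any AE with an onset date that is after the first dose of study drug", with an upper limit of 30 days after the last dose. It adds a same-day rule: "Events where the onset date is the same as the study drug start date are assumed to be treatment-emergent". Earlier events are handled by one sentence: "Pre-treatment AEs will be summarized separately in listing format".
- Protocol 7.4: "A treatment-emergent adverse event (TEAE) is defined as an AE with an onset date on or after the first dose of study drug", with the same 30-day limit. Like the SAP, it does not mention worsening.
- Operations Manual 4.2 (Appendix F of the protocol): "any event that begins or worsens in severity after initiation of study drug through 30 days post-study drug dosing". The sentence describes how the tables by system organ class and preferred term will be built.

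Two recording rules in Protocol 6.1 also bear on the point. Before dosing, only part of the AE spectrum is captured: "SAEs and protocol-related nonserious AEs will be collected from the time the subject signs the study-specific informed consent". For laboratory tests, ECGs, physical examinations and vital signs, "those deemed a clinically significant worsening from baseline will be documented as an AE".

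**The concern.** The definition decides which events enter the main safety tables, and the documents do not agree on it. The Operations Manual binds the conduct of the study (Protocol 8.2), so its sentence cannot be set aside as background. The SAP version history records no decision to drop worsening.

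In the case where the rules differ, an event was already present at screening and became more severe on drug. That is information about the drug. Safety and tolerability are objectives of both parts and feed the choice of dose for Part 2. Arms have 9 or 18 subjects, so a single event is visible in a table. Whether such an event is tabulated should not depend on how a site happens to enter it.

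**Working it through.** The plan gives no figure to reproduce. The check applies the three definitions to the cases that could separate them, and then bounds the effect on a table row.

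**Step 1: apply the definitions.**

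| Case | SAP 9.2.1 | Protocol 7.4 | Operations Manual 4.2 |
|---|---|---|---|
| 1. Onset on a screening day before Day 1, Grade 1; worsens to Grade 3 on drug; kept as one record | Not a TEAE; pre-treatment listing only | Not a TEAE | TEAE |
| 2. Onset on Day 1 before the dose, then worsens | TEAE (same-day rule) | Depends on whether onset is judged by date or by time | TEAE |
| 3. As case 1, but the worsening is entered as a new AE dated after the first dose | TEAE | TEAE | TEAE |

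The SAP and the Operations Manual part only in case 1. It needs two conditions: onset before the date of first dose, and worsening held on the original record.

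**Step 2: who can be in case 1.** The event must be recorded as an AE before dosing. That limits it to SAEs and protocol-related nonserious AEs arising after consent (Protocol 6.1; Operations Manual 4.1), within a Screening period of up to 30 days (Protocol Appendix D). It must be ongoing at the first dose and then worsen. Criteria 11, 12 and 20 (stable pulmonary status, no added-risk condition in the investigator's opinion, stable regimen) would keep out many subjects with an unresolved screening SAE. The documents give no count, so none is assumed here.

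**Step 3: which outputs are involved.** The SAP builds the TEAE overview (9.2.2), the tables by organ class, preferred term, severity and relationship (9.2.3), and the treatment-emergent SAE table (9.2.4) on this definition. No SAP section brings a worsened pre-dose AE back into them.

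**Step 4: size per subject.** The planned arm sizes are 9 or 18 (Protocol 4.1). The combined placebo group has 18 + 9 = 27 (also given in SAP 2.4). One subject left out of a row changes its percentage by at most 1/n:

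- n = 18: 1/18 = 5.6 points
- n = 9: 1/9 = 11.1 points
- n = 27: 1/27 = 3.7 points

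These are maxima. A subject counts once per row (SAP 9.2 and 9.2.3), so a row does not move if the same subject already has another event counted in it. For example, a subject with any other TEAE leaves the overall TEAE rate unchanged, while the Grade 3 or higher row could still move.

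**The case against.** A reader might infer that every worsened pre-dose event is absent from every TEAE table, and that each omission lowers an arm's rate by 5.6 or 11.1 points. The documents do not support either statement.

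- **Data entry.** The loss depends on the worsening staying on the original record, and no document says that sites will do this. Some text points the other way: clinically significant worsening of a study assessment becomes an AE (Protocol 6.1), and so do significant examination findings after the first dose (Operations Manual 3.10). This stands as a limit. It does not close the gap, because neither rule says that an AE already recorded gets a new entry and onset date when it worsens.
- **Other outputs.** The event remains in the pre-treatment listing. Deaths have their own row and listing. The rash AESI section (SAP 9.2.5) selects by a MedDRA query with no treatment-emergent limit, although SAP 9.2.2 places AESIs inside the TEAE overview, so this is unclear. Laboratory worsening shows in shift tables and potentially-clinically-significant counts, and vital-sign worsening in the latter. This stands too, but none of these outputs replaces the TEAE tables.
- **Size.** The row effects are upper bounds, as shown in the working.
- **Which text governs.** Protocol 7.4 agrees with the SAP and leaves the details of the safety analysis to it. The Operations Manual is therefore the outlier, and deleting its worsening clause would also make the texts consistent. This is true. The preference for the wider rule rests on what it captures, and the sponsor has already written that wording.

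**Conclusion.** The inconsistency is real and lies between current texts. Its consequence is conditional: under the SAP, a recorded pre-dose AE with onset before the first-dose date that worsens on drug may be missing from the TEAE tables if the worsening is kept on the original record. Few subjects can be affected, and the row effects are ceilings based on planned arm sizes. The point does not touch efficacy and is a minor one. It is still worth settling, because the present texts let site record-keeping decide whether on-drug worsening is tabulated, and a report that follows the SAP would not match the Operations Manual's description of the same tables.

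**What to change.** Use one definition in SAP 9.2.1, Protocol 7.4 and Operations Manual 4.2: an AE that begins, or worsens in severity, on or after the first dose and within 30 days after the last dose. Keep the SAP's same-day assumption.

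Add to the eCRF guidance that worsening of a recorded pre-dose AE is entered as a new record dated at the worsening. Both changes are useful. The entry rule supplies the date that the definition needs, and the common definition removes the conflict between the documents. Because each subject counts once per row, the extra record does not count a subject twice.

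The cost is a sentence in each of the three texts and a line of site guidance. The downside is that a few more events may be counted as treatment-emergent, which is the cautious direction for a safety table.
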